#### Subsequent areas of progression:

As long as the study participant is on ceritinib as the sole systemic therapy, further stereotactic radiation may be delivered to up to 6 sites or organs at a time. When ceritinib is no longer the systemic agent or when new progressive sites cannot feasibly be treated with stereotactic radiation (e.g., malignant pleural effusion or site previously irradiated), study participation will end. The primary endpoint of progression-free survival will be calculated from the start of treatment to the first episode of progression.

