## 2.0 Study Objectives

The hypothesis is that delivering SABR to patients with persisting tumors 10 weeks after ceritinib will result in superior overall tumor control, prolong PFS for patients and lengthen the duration of ceritinib activity in patients with *ALK*+ lung adenocarcinoma.

Published experience suggests that median PFS for patients who have previously been treated with crizotinib is less with ceritinib than those who have never been treated with crizotinib (7 months vs 10 months) (Shaw et al, NEJM 2014). As a result patients enrolled on this study will be divided into cohorts on the basis of prior exposure to crizotinib.

The primary endpoint of this study will be Progression-Free Survival (PFS); defined as time from initiation of ceritinib to evidence of disease progression by RECIST 1.1, unacceptable toxicity, withdrawal of consent, or discontinuation of the trial for any other reason.

There may be progression in a specific localized region that is amenable to stereotactic radiation. If all existing lesions that enlarge and any new lesions that develop can still be effectively treated with stereotactic radiation, patients will be evaluated for repeat SABR therapy and ceritinib resumed. This will be at the recommendation of the treating physician according to standard practice. This will be defined as Time to 2nd SABR therapy and will be one of the secondary endpoints.

Similarly, if 3rd round of SABR can be safely provided with subsequent resumption of ceritinib, it will be defined as the Time to 3rd SABR therapy.

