### Cohort A (*ALK* inhibitor naive):

**Primary Objective:** To demonstrate the superiority of ceritinib combined with SABR in prolonging median PFS compared to historical control of 10 months

**Primary Endpoint:** Median PFS (as described in section 2.0) for study cohort, expected to be 20 months

**Hypothesis:** The addition of stereotactic radiation in patients with *ALK*+ lung adenocarcinoma receiving ceritinib will enhance efficacy leading to prolongation of time on ceritinib monotherapy.

**Secondary Objectives:** To describe overall survival in study participants  
To describe the time to 2nd and 3rd SABR therapy  
To determine the number of patients with CR, PR or stable disease by RECIST 1.1 criteria at 6 and 12 months

**Secondary Endpoints:** Overall survival  
Time to 2nd SABR treatment, Time to 3rd SABR treatment

PFS at 6 and 12 months from study initiation therapy

**Safety Objectives:** Demonstrate safety of ceritinib followed by SABR.

Safety Endpoints: toxicity and adverse events (CTCAE v.4)

**Hypothesis:** the safety of this combination of targeted therapy and radiation will be as safe as published experience of both these agents.

Cohort B (treated with one prior ALK-inhibitor):

**Primary Objective:** To demonstrate the superiority of ceritinib combined with SABR in prolonging median PFS compared to historical control of 7 months

Primary Endpoint: Median PFS (Time to subsequent systemic therapy) for study cohort, expected to be 14 months.

**Hypothesis:** the addition of stereotactic radiation in patients with ALK+ lung adenocarcinoma receiving ceritinib will enhance efficacy and prolongation of time on ceritinib monotherapy.

**Secondary Objectives:** To describe overall survival in study participants  
To describe the time to 2nd and 3rd SABR therapy  
To determine the number of patients with CR, PR or stable disease by RECIST 1.1 criteria at 6 and 12 months

Secondary Endpoints: Overall survival  
Time to 2nd SABR treatment, Time to 3rd SABR treatment  
PFS at 6 and 12 months from study initiation

**Hypothesis:** The combination of SABR and ceritinib will result in a clinically meaningful overall survival in study participants.

The early application of SABR will be effective in delaying progression which is amenable to SABR but does not require a change in systemic therapy

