### 6.1.6 Progression-Free Survival

Progression Free Survival will be the primary endpoint for this study. If oligoprogression occurs that is amenable to repeat treatment with SABR, the ceritinib will be held and SABR therapy delivered. If the treating oncologist then feels the patient would benefit from continuing the ceritinib that will be permitted. The patient will however be deemed as having progressed even if ceritinib is resumed.

After the initial SABR to persisting lesions if new lesions appear or if existing lesions enlarge but are NOT amenable to SABR (necessitating a change in systemic therapy), the patient will have completed the therapeutic portion of the study.

Time to 2nd SABR is defined as the duration of time from the start of treatment to the time of development of new or enlarging lesions that are amenable to SABR and the progression does not require a discontinuation of ceritinib.

Time to 3rd SABR is defined in patients who have already received two rounds of SABR while on this study as the duration of time from the start of treatment to the time of development of new or enlarging lesions that are amenable to SABR and the progression does not require a discontinuation of ceritinib.

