**Study Design:**

**Purpose:** of this prospective, single-center, two cohort, non-randomized trial is to evaluate the impact of the combination of ceritinib and stereotactic radiation delivered to patients with *ALK*-rearranged adenocarcinoma. The enhanced efficacy of this combination is to be evaluated specifically with regards to prolongation of clinical benefit of ceritinib. We will also evaluate the safety of this combination of targeted therapy and radiation.

For *ALK*-rearranged patients started on ceritinib and treated with SABR to persisting lesions:  
 -PFS compared to published historical results with ceritinib alone PFS=7 month for prior crizotinib treated and 10 month for no previous crizotinib therapy (Shaw et al, NEJM 2014).  
 PFS will be defined as Time to Subsequent Systemic Therapy.

As secondary objectives, we will also report overall survival and time to 2nd and 3rd SABR for each cohort.

	Objective	Endpoint
Primary:	Cohort A: Superiority of ceritinib + SABR median PFS compared to historical control of 10 months (expected to be 20 months)  Cohort B: Superiority of ceritinib + SABR median PFS compared to historical control of 7 months	Cohort A Median PFS defined as time from initiation of ceritinib until disease progression by RECIST 1.1, unacceptable toxicity, withdrawal of consent, or discontinuation of the trial for any other reason including death.  Cohort B: Median PFS defined as time from initiation of ceritinib until disease progression by RECIST 1.1, unacceptable toxicity, withdrawal of consent, or discontinuation of the trial for any other reason including death.
Secondary:	Report Overall survival  Report Time to 2 nd SABR  Report Time to 3 rd SABR  Report proportion of patients CR/PR/stable disease at 6 and 12 months	Overall survival  Time from start of systemic therapy to first day of second course of SABR  Time from start of therapy to first day of third course of SABR  Number of patients with CR/PR/stable disease for 6 and 12 months after initiation
Safety:	Demonstrate safety of ceritinib followed by SABR	Describe toxicity and adverse events (CTCAE v.4) compared to historical controls.

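### The plan gives two rules on whether a first progression that SABR can treat is a PFS event, and the rule printed with the historical comparison leans toward success

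*Combined protocol and SAP*

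**What the plan says.** **First progression is the event.**

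- Section 2.0 defines the primary endpoint as "time from initiation of ceritinib to evidence of disease progression by RECIST 1.1, unacceptable toxicity, withdrawal of consent", or coming off the trial for another reason.
- The Cohort A primary endpoint in section 2.0 refers back to that definition: "Median PFS (as described in section 2.0) for study cohort, expected to be 20 months".
- Section 1.3.3, on subsequent areas of progression, says PFS "will be calculated from the start of treatment to the first episode of progression".
- Section 6.1.6 takes the disputed case itself, oligoprogression treated with SABR: "The patient will however be deemed as having progressed even if ceritinib is resumed".
- Section 8.3 says PFS is already fixed by the time additional SABR is given to new areas.
- Both cohort rows of the section 9.1 endpoint table read "Median PFS defined as time from initiation of ceritinib until disease progression by RECIST 1.1", followed by the other stopping events, including death.

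**Change of systemic therapy is the event.**

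- The prose of section 9.1, immediately after the historical 7 and 10 months: "PFS will be defined as Time to Subsequent Systemic Therapy".
- The Cohort B primary endpoint in section 2.0: "Median PFS (Time to subsequent systemic therapy) for study cohort, expected to be 14 months".

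**Mixed.** The Hypothesis text closing section 2.0 opens with RECIST progression as the primary measure. Later, under the secondary objective on repeat SABR, it treats patients whose new or enlarging lesions can be irradiated as not yet progressed.

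No clause says which rule governs. Section 9.3 gives Kaplan-Meier estimation for PFS and names no test against the historical medians.

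**The concern.** The two rules part for a patient the protocol expects to see: one whose disease progresses at a site SABR can treat, who is re-irradiated and resumes ceritinib. Under one rule the PFS clock stops at that progression. Under the other it runs on until systemic therapy changes.

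The benchmark is PFS on ceritinib alone. If it was measured to first progression or death, setting the later date against it credits the combination with time gained by relabelling an event, without any delay in RECIST progression. Section 9.1 contains both rules, and section 2.0 assigns different ones to the two cohorts. Either could be cited after the data are seen in an open-label trial.

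**Working it through.** **1. The plan's own sample sizes.** Inputs from section 9.2: medians 10 v 20 months (A, n = 18) and 7 v 14 (B, n = 15), two-sided alpha 0.10, power 80%, 36 months' accrual plus 12 months' follow-up. With exponential times and uniform accrual, λ = ln 2 / median and

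P(event) = 1 − [exp(−12λ) − exp(−48λ)] / (36λ).

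This gives null/alternative event probabilities of 0.840/0.623 (A) and 0.917/0.742 (B). A one-sample test on the log hazard needs

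N = [(1.645/√p0 + 0.842/√p1) / ln 2]².

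- A: [(1.795 + 1.066)/0.693]² = 17.0, against 18 stated.
- B: [(1.718 + 0.977)/0.693]² = 15.1, against 15 stated.

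Power by this formula at the stated N is 81.7% and 79.8%. The sample sizes are not in dispute.

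**2. Direction.** For a re-irradiated patient who stays on ceritinib, time to subsequent systemic therapy equals time to first progression plus a further interval, so it is later. The ordering fails for a patient who changes therapy before RECIST progression.

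**3. What limits the size.** The documents do not give the share of first events that are SABR-treatable progressions. It may be small: section 1.3.3 has all gross tumor irradiated after 10 weeks, and its examples of sites that cannot feasibly be treated are "malignant pleural effusion or site previously irradiated". It is not bounded, because section 2.0 permits additional SABR to enlarging lesions. The 64% in section 1.1.4 is progression at known sites, which is a different quantity.

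**4. Illustration (all inputs below are assumptions).** First-progression median equals the historical value, so there is no benefit. A share p of first events is SABR-treatable. Each treatable progression is followed by a further exponential interval of equal or half mean length, with one, two or unlimited repeats. A share q of first events is additional toxicity or withdrawal stops, counted under both rules. The test is a one-sample log-rank at upper-tail 5%, with 200,000 trials per setting.

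Analytic check of the medians at p = 0.2, q = 0:

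- Unlimited equal-length repeats give hazard λ(1 − p), so medians of 10/0.8 = 12.5 and 7/0.8 = 8.75 months.
- One half-length repeat gives S = 1.2x − 0.2x² with x = exp(−λt). S = 0.5 at x = 0.4505, so t = 11.5 and 8.05 months.

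The simulated ranges are 11.5–12.5 (A) and 8.1–8.7 (B).

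False-success rate, %:

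| p | q | First progression, A / B | Time to subsequent systemic therapy |
|---|---|---|---|
| 0.1 | 0 | 3.6 / 3.5 | 5.2–8.7 (both cohorts) |
| 0.2 | 0 | 3.6 / 3.5 | A 8.5–18.4; B 7.4–17.4 |
| 0.3 | 0 | 3.6 / 3.5 | 10.3–34.6 (both cohorts) |
| 0.2 | 0.1 | 1.2 / 1.2 | A 3.5–9.5; B 3.0–9.0 |
| 0.2 | 0.2 | 0.3 / 0.3 | A 1.0–3.7; B 0.9–3.5 |

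**5. Harsher assumptions.** Let 25–75% of first progressions be treatable, with a median added delay of 3–10 months (A) or 3–7 months (B) and no additional stops. A log-hazard Wald test then gives false success of 6.6–79.9% (A) and 7.4–72.6% (B), against 3.4% and 3.3% under first progression. The direction is the same; the size depends on what is assumed.

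**The case against.** The strongest reply is that the intended rule is already clear. Section 6.1.6 is the PFS section, addresses the disputed case directly, and agrees with sections 1.3.3, 8.3, the general definition in 2.0 and both rows of the 9.1 table. Repeat SABR has its own secondary endpoints. The contrary text is one sentence and one parenthesis, and the remark in the Hypothesis text sits under a secondary objective. It stands that most of the text favours first progression. But the contrary rule is printed at the historical comparison and as Cohort B's primary endpoint, so following either as written gives a different analysis.

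Three further points stand as limits:

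- The direction depends on how the historical PFS was defined, which the documents do not say. Section 1.1.2 gives nearly the same figures (10 and 6.9 months) as duration of response, while section 9.2 calls 10 and 7 months PFS.
- The percentages are illustration only. At p = 0.05 with no additional stops they are about 4.3–5.8%, close to nominal. The rows with stops model a hybrid, because the sentences naming subsequent systemic therapy do not say how toxicity, withdrawal or death counts.
- Counting toxicity and withdrawal as events, as the 9.1 table does, costs power. With true progression medians of 20/14 months, one-sample log-rank power is about 78/77% without stops, 67/64% with 10% stops and 51/48% with 20%. That composite is already in the plan and is a separate matter.

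**Conclusion.** The concern holds. The primary endpoint has two incompatible definitions, one of them placed where the historical comparison is made and in the Cohort B endpoint. This rests on the text alone and must be fixed before analysis.

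That the subsequent-therapy rule leans toward success rests on the historical PFS being time to first progression or death, and on re-irradiated patients staying on ceritinib past first progression. The size cannot be determined from the documents. In the illustration the false-success rate can lie below 5% when other stops are common. It always exceeds the first-progression rate with the same stops, because the modelled second date is never earlier.

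**What to change.** State once, for both cohorts, that first RECIST 1.1 progression is a PFS event whether or not the lesion is re-irradiated and ceritinib resumed, as section 6.1.6 already says. Keep the other events, including death, as in the section 9.1 table. Then:

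- remove the subsequent-systemic-therapy wording from the PFS definition in the section 9.1 prose and from the Cohort B endpoint in section 2.0;
- remove from the Hypothesis text in section 2.0 the statement that patients with SABR-treatable lesions count as not progressed;
- make clear that the progression wording in section 5.3.1 and in the bisphosphonate text of section 4.4.1 does not define the PFS event;
- report time to subsequent systemic therapy as a separately named secondary endpoint, with its own rules for death and withdrawal, not tested against 10 or 7 months.

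Sections 2.3 and 9.4 state different end-of-study rules and need reconciling separately; nothing here says which is right. Treatment and study-exit rules are untouched.

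The cost is wording. The stated sample sizes do not change, and first-progression dates come from the imaging scheduled every two cycles (section 5.3.1). New-therapy dates for the secondary endpoint depend on follow-up that section 5.1.16 promises only to attempt. The reported median PFS may be less favourable.

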**STUDY SUMMARY**

Title	Phase II trial of Ceritinib in combination with Stereotactic Ablative Radiation in ALK -rearranged metastatic lung adenocarcinoma
Short Title	Ceritinib and SABR in ALK + lung adenocarcinoma
Protocol Number	XXX
Phase	II
Methodology	Open label, Dual arm
Study Duration	Three years
Study Center(s)	single center
Objectives	Prolongation of progression free survival in lung adenocarcinoma with targeted therapy and radiation
Number of Subjects	33
Diagnosis and Main Inclusion Criteria	Metastatic/locally advanced lung adenocarcinoma harboring a ALK rearrangement
Study Product(s), Dose, Route, Regimen	Ceritinib (LDK378) 450 mg PO daily
Duration of administration	Until progression/intolerance of therapy. Projected 14 months for patients who progressed on crizotinib therapy and 20 months for those who have not been treated previously with an ALK inhibitor.
Reference therapy	Published progression free survival with ceritinib (LDK378) alone
Statistical Methodology	Sample size calculated on the basis of prolongation of progression free survival of patients treated on this protocol compared to published survival data. Kaplan Meier Methods will be used to estimate progression-free survival and overall survival

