**Hypothesis:**

The primary objective is to describe the PFS in patients undergoing study therapy. This is defined as evidence of disease progression by RECIST, unacceptable toxicity, withdrawal of consent, or discontinuation of the trial for any other reason.

Additional SABR to enlarging lesions will be permitted while on ceritinib, but no change in systemic therapy will be allowed. Patients who demonstrate oligo progression and have disease amenable to repeat courses of radiation therapy may resume ceritinib at the discretion of the treating oncologist until a change in systemic therapy is indicated.

The secondary objective of the study is to report overall survival and in *ALK*-positive lung adenocarcinoma. We will use Kaplan-Meier methods to estimate the overall survival. The rate of overall response and its 95% confidence interval will be estimated using exact binomial method. Response duration will be summarized for patients who responded. Descriptive summary statistics like median, 25% and 75% percentiles will be used.

The secondary objective is also to describe the time to subsequent SABR in patients undergoing study therapy. Patients will be retreated with SABR if feasible. After the initial SABR to persisting lesions, if new lesions appear or if existing lesions enlarge but are amenable to SABR, patients will remain on study and listed as not having progressed. This time to 2nd and 3rd SABR will be recorded and reported. The secondary endpoint will be recorded as time to 2nd and (if applicable) 3rd SABR therapy.

The safety objective of this study to report the toxicity profile of the combination of ceritinib and SABR therapy. Both are well tolerated and routinely used in non-small cell lung cancer.

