### 2.3 Definition of end of the Study

The study will end when all 33 patients have evidence of disease progression by RECIST1.1, unacceptable toxicity, withdrawal of consent, or discontinuation of the trial for any other reason.

At the completion or discontinuation of study medication, all patients will be seen within 30 days for an end of therapy evaluation. This will include a safety assessment for AE's SAE's. Any unused medication will be returned.

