#### 6.1.4.3 Evaluation of Best Overall Response

The best overall response is the best response recorded from the start of the treatment until disease progression/recurrence (taking as reference for progressive disease the smallest measurements recorded since the treatment started). The subject's best response assignment will depend on the achievement of both measurement and confirmation criteria.

Target Lesions	Non-Target Lesions	New Lesions	Overall Response	Best Response for this Category Also Requires:
CR	CR	No	CR	≥4 wks. confirmation
CR	Non-CR/Non-PD	No	PR	≥4 wks. confirmation
PR	Non-PD	No	PR	
SD	Non-PD	No	SD	Documented at least once ≥4 wks. from baseline
PD	Any	Yes or No	PD	no prior SD, PR or CR
Any	PD*	Yes or No	PD	
Any	Any	Yes	PD	

* In exceptional circumstances, unequivocal progression in non-target lesions may be accepted as disease progression.
 
Note: Subjects with a global deterioration of health status requiring discontinuation of treatment without objective evidence of disease progression at that time should be reported as "symptomatic deterioration". Every effort should be made to document the objective progression even after discontinuation of treatment.
				

Note: If subjects respond to treatment and are able to have their disease resected, the patient's response will be assessed prior to the surgery.

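### Primary PFS counts toxicity stops, consent withdrawals and any other discontinuation as events, but is tested against a published PFS whose events the plan does not define

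*Combined protocol and SAP*

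**What the plan says.** Section 2.0 measures primary PFS from the start of ceritinib to "evidence of disease progression by RECIST 1.1, unacceptable toxicity, withdrawal of consent, or discontinuation of the trial for any other reason". The hypothesis paragraph later in Section 2.0 repeats it: "This is defined as evidence of disease progression by RECIST, unacceptable toxicity, withdrawal of consent, or discontinuation of the trial for any other reason". The endpoint table in Section 9.1 applies the list to both cohorts and adds death: "disease progression by RECIST 1.1, unacceptable toxicity, withdrawal of consent, or discontinuation of the trial for any other reason including death".

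The comparator carries a different label. The Study Summary gives the reference as "Published progression free survival with ceritinib (LDK378) alone", and Section 9.1 plans "PFS compared to published historical results with ceritinib alone PFS=7 month for prior crizotinib treated and 10 month for no previous crizotinib therapy". Section 9.2 calls the published phase I trial a relevant control but does not say which events its PFS counted.

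On handling, Section 9.3 names Kaplan-Meier methods only. Section 9.10.1 has censoring and discontinuations in its title but says only that missing data are not imputed. The Full Analysis Set is all enrolled patients (9.8.1), and a patient who has taken study drug is not replaced (5.2.3.3). No analysis limited to progression or death is planned.

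Section 6.1.4.3, in its note on symptomatic deterioration, says: "Every effort should be made to document the objective progression even after discontinuation of treatment". Table 5-1 marks no tumour imaging at end of treatment or in long-term follow-up. Section 5.1.16 collects survival and new-therapy information after treatment.

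**The concern.** A patient who stops for toxicity while still responding, or who withdraws consent, has a PFS event on that date under the rule as written. The event list is in substance the stop-treatment rule of Sections 2.2.1 and 9.1 reused as an efficacy endpoint.

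If the published 10 and 7 months count only progression or death, poor tolerability and withdrawals shorten the study's median without shortening the benchmark in the same way. A true delay in progression could then miss the superiority objective, and a short result could not be traced to tumour control. Cohorts of 18 and 15 leave little room for a few such events.

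This is separate from the conflict among first progression (Section 1.3.3), time to subsequent systemic therapy (Section 9.1, and Section 2.0 for Cohort B) and the composite. Choosing between the first two would still leave open how a stop without progression is scored.

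**Working it through.** **Inputs from Section 9.2.** Cohort A: 18 patients, median 10 against 20 months. Cohort B: 15 patients, median 7 against 14 months. Both: two-sided 0.1, 80% power, 36 months accrual, 12 months follow-up. The documents give no rate of stopping without progression, so 5%, 10% and 20% per year are assumed.

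**Step 1: reproduce the plan's figure.** With exponential times, uniform accrual and hazard L = ln 2 / median, the probability of an event by the analysis is

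P(L) = 1 − [exp(−12L) − exp(−48L)] / (36L).

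- A: 0.840 under the null, 0.623 under the alternative. N = [(1.645/√0.840 + 0.842/√0.623) / ln 2]² = 17.04, rounded up to 18.
- B: 0.917 and 0.742. N = [(1.645/√0.917 + 0.842/√0.742) / ln 2]² = 15.11. Power at 15 patients is 79.8%.

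The stated sizes reproduce from the two medians alone. There is no separate allowance for stops without progression.

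**Step 2: add stops.** Treat 20 and 14 months as progression-or-death medians, which is an assumption taken up under the objection. With p stopping per year, independently of progression:

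- stop hazard h = −ln(1 − p)/12 per month
- composite median = ln 2 / (ln 2/m + h)
- share of composite events that are stops = h / (ln 2/m + h)

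For A at 10% per year, h = 0.00878 and ln 2/20 = 0.03466. The composite median is 0.6931/0.04344 = 16.0 months, and the share is 0.00878/0.04344 = 20%.

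**Step 3: power.** Simulated trials, Wald test on the log exponential rate, two-sided 0.1. With no stops, power is about 78% (A) and 76% (B). Ranges show the spread between repeat runs.

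| Stops per year | Cohort | Composite median (months) | Share of events that are stops | Power, stops as events | Power, stops censored |
|---|---|---|---|---|---|
| 5% | A | 17.8 | 11% | 64–65% | 76% |
| 10% | A | 16.0 | 20% | 50% | 73–74% |
| 20% | A | 13.0 | 35% | 22–23% | 69% |
| 5% | B | 12.9 | 8% | 66–67% | 74% |
| 10% | B | 11.9 | 15% | 56% | 72–73% |
| 20% | B | 10.2 | 27% | 35% | 68–69% |

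The simulated test is slightly conservative (about 3.5% rejections under the null), so its no-stop power sits below the 82% and 80% of the Step 1 formula. That formula shows the same pattern: with a 20% share of stops in A, it gives 57% counted against 79% censored.

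**Step 4: direction.** If ceritinib plus SABR did nothing and progression-or-death medians were 10 and 7 months, counted stops would pull the composite below those values. A false claim of superiority becomes less likely.

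**The case against.** The strongest reply is that 20 and 14 months may already be composite medians. The Study Summary projects 14 and 20 months as time on drug until progression or intolerance, and Section 2.0 ties Cohort A's 20 months to its own composite definition. For Cohort B, Section 2.0 ties 14 months to time to subsequent systemic therapy, while the Section 9.1 table gives Cohort B the composite. If composite medians were meant, the stated power stands and Step 3 does not apply. This objection holds. It leaves the comparison with published PFS untouched.

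The stop rates also have no anchor. Section 1.6 reports the lowest gastrointestinal toxicity at the protocol dose, and Table 4-3 reduces dose before stopping for many toxicities. On the other side, the plan itself provides for stops without progression: Table 4-3 requires permanent discontinuation for treatment-related pneumonitis of any grade, and Section 4.3 makes discontinuation the default after interruptions beyond 28 days. The figures are therefore illustrations over a range.

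The composite can also be defended as fitting the aim of longer time on ceritinib, and it avoids some informative censoring. That supports keeping it, under its own name, beside PFS.

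A reader might infer three stronger points that the documents do not support:

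- That closing the trial turns continuing responders into events. The wording sits in a list of patient-level reasons, Section 2.3 says "The study will end when all 33 patients have evidence of disease progression by RECIST1.1" or has met another listed reason, and the reproduced sample size treats event-free patients as administratively censored.
- That a stop is scored as failure of SABR. SABR begins only after at least 10 weeks of ceritinib, so earlier stops occur without it. What is scored is the whole strategy.
- That the distortion certainly falls on the study side alone. That depends on the published event definition, which the documents do not give.

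**Conclusion.** The point holds. As written, the main definition of primary PFS is time to treatment failure, no rule censors stops without progression, and the result is tested against medians labelled PFS. If the published PFS counts progression or death only, the comparison is biased against the study treatment. It costs power and does not inflate false positives.

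The size is conditional. At 5%, 10% and 20% stops per year, counting them leaves power of about 65%, 50% and 22% in Cohort A and 66%, 56% and 35% in Cohort B, against roughly 76% to 68% across both cohorts if they are censored. This assumes exponential times, independent stops, stop rates not found in the documents, and 20 and 14 months as progression-or-death medians. On the composite reading of those medians, only the mismatch of definitions remains. The conservative direction applies to the composite alone. Time to subsequent systemic therapy would pull the other way, because progression treated with SABR would not count.

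**What to change.** - **Section 2.0 (definition, both cohort endpoints and the hypothesis paragraph) and the Section 9.1 text and table:** define primary PFS as time from first ceritinib dose to first RECIST 1.1 progression or death from any cause. State the event definition behind the published 10 and 7 months and match it.
- **Section 9.2:** say which endpoint the 20 and 14 months describe.
- **Section 9.10.1:** censor patients who stop without recorded progression or death at their last adequate tumour assessment. Use standard-of-care scans after stopping where available, in line with Section 6.1.4.3.
- **Section 9.3:** report the present composite as a secondary endpoint named time to treatment failure.

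The cost is wording, plus recording scans already done in usual care for the few patients concerned. No treatment changes. Some informative censoring remains, and the retained composite makes it visible.
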